Aim 2: To determine how slightly-thick and mildly-thick liquids flow and whether they reduce aspiration compared to thin liquids in patients with base of tongue cancer. We will collect concurrent videofluoroscopic x-rays of swallowing and physiological measures of tongue pressure in patients with head and neck cancer using thin, slightly- and mildly-thick liquid barium stimuli. This appointment will occur approximately 3-6 months after the completion of the participants' radiation schedule. Significance: This will demonstrate the impact of consistency on bolus flow through the mouth and pharynx, controlling for the forces used to initiate flow and propel the bolus. Additionally, the data collected will aid in characterizing swallow physiology after completion of radiation therapy.

Aim 3: To determine whether the use of starch vs. gum thickeners impact the results of aims 1 and 2
The thickened liquids used for aims 1 and 2 will be prepared using both starch- and gum-based thickeners. Additionally, we will collect measures of salivary flow to control for possible interactions between thickener type and oral dryness on the results. Significance: Individuals may find one thickener more palatable or comfortable to swallow. Understanding this may impact compliance, swallowing safety and quality of life.

3. Methods

Participants:

The protocol will involve a single sample of adults, aged 18 or older with an initial cancer diagnosis of base of tongue cancer (T1-T3, N0-N2c, HPV + or -). The eligibility criteria will include completion of bilateral radiation therapy to the neck 3 months prior to enrollment, and removal of enteral feeding tube.

Participants will be asked to attend appointments and complete all data collection sessions described in this protocol. Participation involves two appointments, and two follow-up phone calls.

Exclusion Criteria:

- Participants will be accepted into the study provided they have no previous health condition known to cause swallowing impairment (e.g., stroke; brain injury; neurodegenerative disease).
- Individuals with a previous history of radiation to the head and/or neck area (prior to the current radiation treatment) will be excluded from this study given the possibility of long-term radiation effects to the swallowing apparatus.
- Individuals with a previous cancer diagnosis will be excluded from the study.

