- Participants who do not show impaired swallowing safety on thin liquids in the videofluoroscopy (Penetration Aspiration Scale scores of 1 and 2) will be withdrawn from the study.
- Participants who have had, or have a planned neck dissection will be excluded.
- Individuals with tracheostomy *in situ* will be excluded from the study.
- Individuals with cognitive communication difficulties that preclude the understanding of the protocol or following study instructions will be excluded from the study.
- Due to the requirement to swallow stimuli containing starch based thickeners, which carry a significant carbohydrate load, individuals with Type 1 Diabetes will be excluded.
- Individuals with known allergies to latex, dental glue or barium will be excluded, due to the probability that these items will come into contact with the oral mucosa during data collection.
- Children and pregnant women will be excluded from the study due to the use of radiation
- Occupational exposure to radiation exceeding half the limit specified for Ontario exposed workers within the past 12 months.

These exclusion criteria will be confirmed using a self-report questionnaire form at the time of intake into the study (see standard operating procedures [SOP], provided as an additional study document). Any questions will be clarified through discussion with the research assistant responsible for participant intake, and, where necessary with the principal investigator.

Recruitment:

This is a preliminary study that will demonstrate feasibility for a future planned extension. We propose to recruit 10-12 participants. Potential participants will be identified by study Co-PIs [name] and [name] through the current radiation therapy clinics and base of tongue cancer caseloads at Princess Margaret Cancer Centre.

Stimuli:

An array of barium and non-barium stimuli has been developed for this study. These stimuli include thin, slightly-thick and mildly-thick liquids, defined using the International Dysphagia Diet Standardisation Initiative (IDDSI) gravity flow measures. The barium stimuli used for videofluoroscopy will be prepared using E-Z-Paque® barium in 20% w/v barium concentration with starch and gum-based thickening agents (Nestlé Resource® ThickenUp® and ThickenUp Clear®). The non-barium stimuli will be prepared using Nestle's Lemon Splash® lemon-flavoured water and the same starch and gum-based thickening agents

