Participants will be asked to swallow a series of thin, slightly-thick and mildly-thick barium stimuli 1 (3 boluses each of 5 stimuli, for a total of 15 boluses) in videofluoroscopy, with concurrent measurement of tongue-palate pressure. Videofluoroscopy will be performed at optimal temporal resolution (30 pulses/second) and captured at 30 frames/second. The stimuli will be presented in a randomized design, blocked by stimulus type. Participants will be allowed to take natural sized sips of each stimulus from cups containing 40 ml. Sip volume and mass will be calculated, by weighing the cups prior to and after the videofluoroscopic assessment.

Data Processing:

The tongue-pressure waveform will be segmented using an automatic segmentation algorithm developed previously in the PI's lab. Similarly, the videofluoroscopy recordings will be spliced into single bolus clips and the audio channel will be muted to remove cues that might bias rating. Blinded videofluoroscopy rating will then be performed in duplicate by trained raters in the [name] Lab following established procedures (see SOP provided as an additional study document). Discrepancies between raters will be flagged and resolved at consensus meetings, as required. These procedures will yield a

large number of parameters for each swallow. We will use established measures within our lab to collect and analyze measures related to kinematics and residue.

[figure not shown]
Follow-up phone calls: If deemed appropriate, the participant may be offered the opportunity to complete a follow-up component. For those willing to participate, this optional experiment will involve two follow-up telephone calls (at 2 weeks and 3 months following the videofluoroscopy) to determine compliance with use of thickened liquids recommended following the videofluoroscopy (see study instruments provided for questionnaires).

Data Analysis:

For Aim 1, we will compare hedonic ratings for the different stimuli using a univariate ANOVA. It is hypothesized that ratings will be significantly better for the thin and slightly thick stimuli compared to the mildly-thick stimuli, and that a preference will be seen for the gum compared to the starch thickened liquids.

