For Aim 2, blinded videofluoroscopy rating will be performed in duplicate, and discrepancies between raters will be flagged and resolved at a consensus meeting. The frequency of aspiration will be explored with the thin stimuli and compared to the prevalence of aspiration when thickeners are introduced using chi-square statistics.

We will model the impact of stimulus on two timing measures of pharyngeal bolus flow from the videofluoroscopy (i.e., a) the interval from the bolus passing the mandibular ramus until laryngeal vestibular closure; b) the interval from the bolus passing the mandibular ramus until entering the upper esophageal sphincter) and on measures of post-swallow residue (Normalized Residue Ratio Scale). The Saxon test results regarding oral dryness will be used as a covariate for all analyses, as illustrated in the Figure below:

A path analysis approach will be used to first identify differences in tongue pressure across stimuli

(Question 1). If confirmed, this potential modulator will be added to the Question 2 model as a covariate (Question 3). The planned analyses will involve linear mixed model repeated measures ANOVAs with a factor of stimulus.

For Aim 3, we will use qualitative methods to describe participant reports of adherence to the prescribed thickener. Information from the quality of life and performance status scales collected in session 1 will be used to inform our understanding of variations on patterns of thickener acceptance.

4. Risks and Benefits

Risks

The following risks will be disclosed to all participants prior to obtaining their consent to participate:

- a) Participants may experience local mucosal irritation from the glue on the adhesive strip used to attach the tongue-pressure bulbs for data collection. The glue usually wears off within 90 minutes following the conclusion of data collection. In the incidence that participants are unable to tolerate the attachment of the sensors, we will use the IOPI tongue bulbs to collect tongue measurements, and collect videofluoroscopic data using the same protocol.
- b) Participants may dislike the taste or texture of some of the thickened liquid stimuli in the study. Participants will be reminded that they are free to discontinue participation at any time.

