- c) Participants may experience some fatigue during the videofluoroscopy data collection session. Participants will be reminded that they should disclose any fatigue or discomfort to the research team, and that they are free to discontinue any particular session or to withdraw from the study at any time.
- d) Participants will receive additional exposure to radiation during the videofluoroscopy, in addition to their recent radiation treatment protocol. Based on a previous videofluoroscopic study that we have conducted in healthy adults, the study is expected to involve 118+/-18 seconds of radiation exposure (Molfenter & [name], 2013), with an associated dose estimate of <0.35 milliSieverts. Moro and Cazzani showed that this dose (0.35mSv) corresponds to a risk of 1 in 39,000 of developing a radiation-induced stochastic effect from a videofluoroscopy. We will use a 2-minute warning bell to alert the data collection team to exposure time, and will terminate the protocol at the first opportunity following the bell.
- e) Aspiration (entry of material into the airway) is a possible risk during the videofluoroscopic swallowing study that will be performed. This risk is always present for videofluoroscopic swallowing studies, which are intended to document the presence and severity of swallowing abnormalities, including (but not limited to aspiration). When aspiration is observed, standard procedures will be followed to encourage coughing and throat clearing to expel the aspirated material. The protocol will be terminated immediately. Any participant who experiences aspiration will be counseled regarding aspiration prevention strategies and aspiration-risk following the videofluoroscopy.
- f) Choking is an extremely unlikely event. However, in the event of choking, routine emergency procedures will be followed. All study personnel carry current CPR certification.

g) In the unlikely event that an incidental finding is noted on the videofluoroscopy (such as a diverticulum or a mass) the attending SRRL licensed speech-language pathologist will consult the on-call radiologist and generate a clinical report documenting the observation. These findings will be communicated with the participant as per usual clinical practice and follow up with their physician will be recommended.

Benefits

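### Aim 2 names only a chi-square test for aspiration, although the same 10-12 people supply the thin and the thickened boluses; a pre-specified within-participant comparison should replace it

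*Combined protocol and SAP*

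**What the plan says.** Aim 2 asks whether slightly-thick and mildly-thick liquids reduce aspiration relative to thin. The whole analysis of that question is one sentence in section 3, Data Analysis: the frequency on thin will be explored and "compared to the prevalence of aspiration when thickeners are introduced using chi-square statistics".

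The design is a single sample: "We propose to recruit 10-12 participants" (section 3, Recruitment). In Session 2 each person is planned to take "3 boluses each of 5 stimuli, for a total of 15 boluses", in random order, blocked by stimulus. Section 2, Aim 3 adds: "The thickened liquids used for aims 1 and 2 will be prepared using both starch- and gum-based thickeners".

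The timing and residue outcomes are treated differently. After describing those models and the tongue-pressure question, the same section says: "The planned analyses will involve linear mixed model repeated measures ANOVAs with a factor of stimulus". Aspiration is not named there.

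Three other rules decide which boluses and people reach the comparison:
- Section 4, Risks, item e, on what happens when aspiration is observed: "The protocol will be terminated immediately".
- Section 4, Risks, item d: after a 2-minute warning bell the team "will terminate the protocol at the first opportunity following the bell".
- Section 3, Exclusion Criteria: people whose swallowing safety on thin liquid is not impaired on videofluoroscopy (Penetration Aspiration Scale 1 and 2) are withdrawn.

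Section 4, Benefits nevertheless expects some participants to aspirate and also to show safer swallows on thickened stimuli.

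**The concern.** The plan does not say whether a bolus, a stimulus or a person is counted, whether the four thickened stimuli are pooled, whether the comparison is paired, or what the denominators are. The default meaning of a chi-square test is a comparison of independent groups, and here there are none: the same people are on both sides. Counted per bolus, such a test treats repeated swallows by one person as independent. Counted per person, it discards the information on who changed.

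At stake is the one analysis that answers whether thickening reduces aspiration, in a pilot meant to support a later extension. Left as it is, the unit and denominator can be chosen after the data are seen, and the test's error has no fixed direction.

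**Working it through.** The plan gives no alpha, power, aspiration rate or effect size, so it has no error figure to reproduce. All rates below are assumptions; the level is two-sided 5%.

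**1. Denominators.** 3 x 5 = 15 boluses, as stated. One thin stimulus plus 2 consistencies x 2 thickeners makes 5 stimuli, hence 3 thin and 12 thickened boluses per person. This split is inferred, but it matches the stated five. For 10-12 people: 30-36 thin and 120-144 thickened boluses.

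**2. Bolus-level independent chi-square, all boluses given, no stimulus effect.** Model: logit(risk) = m + person effect + person-by-stimulus effect, with m = -2, -1 or 0 (12%, 27% or 50% before random effects), n = 10 or 12, and 4,000 simulated studies per setting. For n = 12, m = -1:

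| Person SD | Person-by-stimulus SD | Rejection |
|---|---|---|
| 0 | 0 | 4.4% |
| 1 | 0 | 3.9% |
| 2 | 0 | 1.5% |
| 3 | 0 | 0.8% |
| 1 | 1 | 6.8% |
| 2 | 1 | 3.9% |
| 1 | 2 | 12.6% |
| 2 | 2 | 9.8% |

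Over all settings: 0.5-7.2% with person-by-stimulus SD up to 1, and 9.1-13.0% with SD 2. A person effect shared by all stimuli cancels in the contrast, so the test is too cautious. A person-by-stimulus effect does not cancel, so the test becomes too liberal. A beta-binomial model gave the same pattern: with propensity shared across stimuli, about 3% at an intraclass correlation of 0.2, down to 0.4-0.8% at 0.6; with propensity drawn independently for each person and stimulus, an extreme structure, about 10% up to 19%.

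**3. Participant level, equal opportunity (thin v one thickened stimulus).** Suppose 9 of 12 aspirate on thin and 4 of 12 on thickened. Pearson: pooled proportion 13/24 = 0.542; (0.750 - 0.333)^2 / [0.542 x 0.458 x (2/12)] = 4.20, p = 0.041, whatever the pairing. McNemar depends on who changed:
- 5 v 0 discordant: exact p = 2 x 0.5^5 = 0.0625; asymptotic p = 0.025.
- 6 v 1: exact 0.125; asymptotic 0.059.
- 8 v 3: exact 0.227; asymptotic 0.13.

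**4. Within-participant alternative, same null settings.** A sign-flip test on (proportion aspirated on thin) minus (proportion on all thickened) rejects about 1.6-5.3%. Thin v one stimulus, 3 v 3 boluses, rejects 0.2-3.3%. With thin at m = 0 and thickened 1.4 logits lower, power is about 16-84% for the pooled contrast and 7-61% for 3 v 3.

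**5. If sessions end at the first aspiration.** With an equal, independent risk p per bolus, expected boluses per person are [1 - (1-p)^15]/p. At p = 0.1 this is (1 - 0.206)/0.1 = 7.9. Twelve people would then give about 19 thin and 76 thickened boluses, and 59% would reach a thin bolus. At p = 0.3 the figures are 8, 32 and 30%. In the model of step 2, 2.0-7.6 of 15 boluses are given on average, and only 0.5-5.8 of the 10-12 people have both thin and thickened data. Among those people, thin minus pooled thickened is biased by about +1 to +5 points; over all boluses pooled, the bias is about zero.

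**6. Selection on the thin result, all boluses given, no true effect.** If only people who aspirate on thin were kept, at an independent 10% risk the thin proportion becomes 0.1/(1 - 0.9^3) = 0.1/0.271 = 37%, against 10% on thickened. Across the model settings the spurious benefit is about 5-30 points. If retention needs only a milder impairment, 1, 2 or 3 logits easier to reach than aspiration, it averages about 5.5, 2 and 1 points (maxima 15, 8 and 4).

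**The case against.** The best defence has four parts.

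- *Chi-square statistics may include a paired form such as McNemar.* This stands. The documents do not show that an unpaired test will be used; they show that nothing rules it out.
- *The unit is hinted at.* Data Processing splits recordings into single-bolus clips and yields parameters per swallow. That settles the rating unit but not the analysis unit. On the bolus reading the error is near or below nominal unless person-by-stimulus variation is large. This also stands and limits the harm.
- *The mixed-model sentence could cover aspiration.* It follows the timing, residue and tongue-pressure questions, and aspiration has its own named test. A linear model is also not the natural choice for a yes/no outcome.
- *This is a pilot, and the wording is exploratory.* True, and no decision rule is attached. The comparison still carries Aim 2.

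Stronger readings are tempting but not supported. Pooling any aspiration over 12 thickened boluses against 3 thin would, at an equal, independent 10% risk per bolus, give 1 - 0.9^12 = 72% v 1 - 0.9^3 = 27%, and simulated false-positive rates of about 3-71%; the plan never states that reading. A reader might also infer from "the study is expected to involve 118+/-18 seconds of radiation exposure" that the bell will cut short a large share of sessions. That figure comes from healthy adults, the meaning of the +/- is not given, and passing two minutes does not say how many boluses are lost.

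**Conclusion.** The point holds as a specification and method fault that should be fixed. An independent-samples chi-square does not fit one sample measured under every stimulus, and a better-matched analysis costs no data. The bolus-level false-positive rate would be about 0.5-7% with moderate assumed variation and 9-13% with large person-by-stimulus variation, so a general claim of inflated false positives is not supported. These figures assume logit-normal variation, baselines of 12-50% and all 15 boluses given.

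Two limits lie outside the choice of test. If item e of the Risks is applied as written, few people have both thin and thickened data, and no paired test is usable. The +1 to +5 point bias applies only to those few people, not to the pooled comparison. Withdrawal on the thin result favours thickeners, but a reader should not take 5-30 points as the expected size: the rule removes scores of 1 and 2 and does not require aspiration, and under the milder assumptions tested the average is about 1-6 points.

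**What to change.** 1. Replace the chi-square with a pre-specified within-participant comparison: each person's proportion of boluses aspirated on thin minus the proportion on all thickened boluses, with a sign-flip test or paired interval labelled exploratory. Proportions already allow for 3 v 12 boluses. Report thin v each of the four thickened stimuli as paired differences with 95% intervals, which also serves Aim 3.
2. Report boluses given per stimulus and the number of participants with both thin and thickened data.
3. Separately, reconcile section 4, Risks (termination when aspiration is observed, and after the bell) with the 15 boluses of Session 2 and with section 4, Benefits. If sessions do end at first aspiration, report aspirated/given counts per stimulus descriptively, without a test.
4. State that withdrawal on the thin result selects on one side of the contrast and tilts it toward a thickener benefit, by an amount that depends on how much milder than aspiration the retained impairment is.

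Cost: items 1 and 2 are wording and need no new data. Item 3 needs a protocol clarification, and item 4 a stated limitation. The paired test is somewhat conservative and precision stays low. If exact McNemar were used at participant level, at least 6 people would have to change in one direction and none in the other (2 x 0.5^6 = 0.031).

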(Nestlé Resource® ThickenUp® and ThickenUp Clear®). All stimuli will be prepared in the Swallowing Rehabilitation Research Laboratory not longer than 6 hours prior to scheduled use, according to a strict standard operating procedure (refer to additional reference documents). Following preparation, stimuli will be stored in the swallowing lab until needed. Barium stimuli will be transported to the radiology suite at Toronto General Hospital in a cooler, as per routine clinical procedures.

Data to be collected from each participant:

The following types of data will be collected from participants:

- a) An intake questionnaire noting age, sex, ethnicity and race data and confirming eligibility based on the absence of reported exclusion criteria.
- b) During the intake process, we will review a list of conditions that could alter the results of the research study and identify whether any of these conditions apply. This will include disclosing the use of any medications that the participant is currently taking, in order to allow us to control for the possible influence of medication on oral sensory and motor function. Medications do not qualify as the basis for exclusion. However, it is important for us to collect information regarding the use of benzodiazepines and neuroleptic medications that are known to have possible effects on swallowing, particularly with respect to causing xerostomia (dry mouth).
- c) Palatability ratings for thickened liquids (with barium and without barium).
- d) The MD Anderson Dysphagia Inventory (a quality of life scale related to dysphagia)
- e) The Performance Status Scale – Head and Neck (a scale capturing dysphagia and diet status)
- f) The University of Washington Quality of Life Revised Version 4 (UW-WOL-R4).
- g) Tongue-pressure waveform data, collected at the anterior, middle and posterior palate using the 3-bulb tongue-pressure bulb array of the KayPENTAX Swallowing Signals Lab. If the participant is unable to tolerate the attachment of the sensors, we will measure tongue strength using the Iowa Oral Performance Instrument (IOPI). This approach does not include adhered attachments to the oral mucosa.
- h) A measure of stimulated saliva (the Saxon Test), using a 2x2 inch of folded gauze that is chewed for 2 minutes, expectorated and then weighed prior to being discarded.
- i) A videofluoroscopy recording of swallowing collected at a pulse rate of 30 pulses per second and video capture at 30 frames per second.

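### Aim 2 promises a force-controlled effect of consistency on flow, but tongue pressure enters the model only if an undefined Question 1 result is confirmed, so that estimate may not be produced

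*Combined protocol and SAP*

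**What the plan says.** In section 2, the significance statement for Aim 2 sets no condition: "This will demonstrate the impact of consistency on bolus flow through the mouth and pharynx, controlling for the forces used to initiate flow and propel".

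Section 3, Data Analysis, takes the Aim 2 flow outcomes (two timing intervals and post-swallow residue) in steps. Question 1 comes first: "A path analysis approach will be used to first identify differences in tongue pressure across stimuli". The next step depends on it: "If confirmed, this potential modulator will be added to the Question 2 model as a covariate (Question 3". The planned models are repeated-measures linear mixed models with stimulus as the factor. Oral dryness from the Saxon test, by contrast, is a covariate in every analysis.

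The sample is small ("We propose to recruit 10-12 participants") and the study is presented as a pilot: "This is a preliminary study that will demonstrate feasibility for a future planned extension". Each participant is to give repeated swallows: "3 boluses each of 5 stimuli, for a total of 15 boluses". For anyone who cannot tolerate the palate sensors, section 3 provides a substitute: "we will measure tongue strength using the Iowa Oral Performance Instrument (IOPI"). That gives a tongue-strength value, not a pressure recorded during each swallow.

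**The concern.** The aim and the analysis rule do not match. If Question 1 is not confirmed, the rule as written ends at Question 2, the effect of stimulus without pressure. That is the total effect of changing the liquid, including any part that acts through a change in tongue force. Aim 2 asks for the effect with force held constant, which is Question 3. These are different quantities, and a preliminary result in a small sample decides whether the second is estimated at all.

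The criterion is also the wrong one for deciding on adjustment. It asks whether mean pressure differs by stimulus. Pressure could vary from swallow to swallow and drive timing and residue with no difference in stimulus means, and adjustment would then still improve precision.

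At stake is whether the pilot delivers the estimate named in its own aim.

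**Working it through.** **No figure to reproduce.** The plan states no power, effect size, standard deviation, within-person correlation or alpha. The text gives no threshold for confirmation and does not name the pressure parameter or bulb site to be tested. Everything below on how often adjustment is triggered therefore rests on assumptions, shown as a range.

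**Inputs.** From section 3: n = 10 to 12; 5 stimuli × 3 boluses = 15 swallows per person. Assumed: two-sided alpha 0.05; confirmation means statistical significance.

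**Step 1. Paired contrast, thin versus mildly thick.** Let dz be the mean within-person pressure difference divided by the SD of those differences. The test is a t test on n − 1 df with noncentrality dz × √n. For dz = 0.5, noncentrality is 0.5 × √10 = 1.58 against a critical value of 2.262 (9 df), and 0.5 × √12 = 1.73 against 2.201 (11 df).

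| Assumed dz | Triggered, n = 10 | Triggered, n = 12 |
|---|---|---|
| 0.3 | 14% | 16% |
| 0.5 | 29% | 35% |
| 0.8 | 62% | 71% |
| 1.0 | 80% | 88% |

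The even-odds point is dz of about 0.69 at n = 10 and 0.62 at n = 12.

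**Step 2. Test across all five stimuli.** For a repeated-measures F test on person-by-stimulus means, noncentrality is n × k × f² / (1 − ρ) with k = 5, on 4 and 4(n − 1) df, sphericity assumed. For f = 0.25, ρ = 0.5 and n = 10 this is 10 × 5 × 0.0625 / 0.5 = 6.25.

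| Assumed f | Assumed ρ | Triggered, n = 10 | Triggered, n = 12 |
|---|---|---|---|
| 0.10 | 0.3 | 8% | 9% |
| 0.10 | 0.8 | 19% | 22% |
| 0.25 | 0.3 | 31% | 38% |
| 0.25 | 0.5 | 43% | 52% |
| 0.25 | 0.7 | 67% | 77% |
| 0.25 | 0.8 | 86% | 93% |
| 0.40 | 0.3 | 72% | 81% |
| 0.40 | 0.8 | about 100% | about 100% |

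**Step 3. What a failed test would show.** The 95% confidence interval for the paired difference has half-width t/√n in SD units: 2.262/√10 = 0.72 and 2.201/√12 = 0.64. Even an observed difference of exactly zero would leave true differences of that size inside the interval. Failure to confirm does not show that force is equal across liquids.

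**Step 4. Fewer participants with sensor data.** Only those who tolerate the sensors contribute to Question 1; no rate is given. If 6 did (assumed), the paired figures fall to 17% at dz = 0.5, 36% at 0.8 and 51% at 1.0.

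**Step 5. Why equal means do not make adjustment pointless.** Write flow = stimulus effect + γ × pressure + error. If mean pressure is the same for every stimulus, total and force-constant effects coincide, but the residual variance is σ² with pressure in the model and σ² + γ² × Var(pressure) without it. The Question 1 criterion says nothing about γ.

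**The case against.** **A reader might infer that the force-controlled answer would usually never be produced.** The documents do not support this. With large pressure differences or high within-person correlation, adjustment would mostly be triggered; the tables run from 8% to nearly 100%. A mixed model on all swallows might also be more sensitive than the paired test, depending on variance components that nobody has stated.

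**A reader might also infer that the unadjusted effect will be passed off as force-controlled, or that the rule yields a biased estimate of a known size.** The plan separates Question 2 from Question 3 and nowhere says that one will be relabelled as the other. Averaging unadjusted results from some trials with adjusted results from others mixes two estimands, so a single bias figure would mislead.

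**The adjusted model is not free of bias either.** Participants take natural-sized sips, and sip volume could affect both pressure and flow. This stands, and the fix needs a caveat for it.

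**Remaining points.** Stepwise testing of a mediating path is a recognised, if dated, approach, and this is a feasibility pilot. A figure to which the Data Analysis section refers is not reproduced in the text available, so the rule may be specified more fully there. The plan announces no formal comparison of Questions 2 and 3, and gives no rate of sensor intolerance.

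These points limit the claim but leave the mismatch with Aim 2. Pilot status favours reporting both estimates over choosing between them with an unpowered test.

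**Conclusion.** The concern holds as a mismatch between the aim and the analysis rule: Aim 2 promises "controlling for the forces used to initiate flow and propel the bolus" unconditionally, while the Data Analysis section makes that control depend on Question 1. The force-controlled estimate may therefore not be produced. It would often be missing if pressure differences are small to moderate (triggered 29–35% of the time at dz = 0.5), and less often if they are large (62–71% at 0.8, 80–88% at 1.0). These figures assume a paired test at two-sided alpha 0.05 and all 10 to 12 participants giving sensor data.

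Two parts of the conclusion need no assumed effect size: the rule as written can leave the aim unanswered, and a difference in stimulus means is not a sound criterion for including pressure. The change should be made; the point does not invalidate the study.

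**What to change.** In section 3, Data Analysis:

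- Delete the condition. For each timing and residue outcome, always report the stimulus model without tongue pressure (Question 2, total effect) and with per-swallow tongue pressure (Question 3, effect with force held constant), both with confidence intervals.
- Name the pressure parameter and bulb site in advance. Report Question 1 as description, not as a gate.
- Fit the two models on the same swallows with sensor data, so that a difference between them is not a difference in who is included. Keep IOPI-only participants in an additional all-participant version of the unadjusted model.
- State that the adjusted estimate assumes no unmeasured common cause of pressure and flow. Sip volume, already to be derived from cup weights, is a candidate covariate; say whether those weights give a value per swallow or only an average per cup.

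The cost is a few sentences, one extra model per outcome and an adjusted estimate that carries this caveat. No new data are needed.
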